10.5 PROTOCOL DEVIATIONS

Protocol deviations and their classification (minor/major) will not be summarized.

Protocol deviations will be classified as major and minor as specified in the Protocol Deviations Management Plan. Patients with major protocol deviation will be identified and documented before the database lock.

Review Status: Final Version: 2.0 Version Date: 02JUN2022

10.6 Patient Characteristics

Patient characteristics will be summarized for safety population.

10.6.1 Baseline and Demographic Characteristics

Descriptive statistics for continuous variables (age at screening, height, weight at baseline, and BMI [body mass index]) and frequency counts and percentages for categorical demographic variables (gender, ethnicity, race, Globo-H score, and Eastern Cooperative Oncology Group [ECOG]) performance will be summarized by study part, and cohort using the safety population.

BMI will be derived as: BMI [kg/m²] =weight[kg]/(height[cm]/100)².

Height reported in inches will be converted to centimeters as: height [cm] = height [in] * 2.54.

Demographic and baseline characteristics will be provided in a listing.

10.6.2 CANCER DIAGNOSIS HISTORY

Part A

Time since initial diagnosis (months), tumor size at first diagnosis (mm), tumor type and location, TNM stage of disease at diagnosis and at study entry, presence and location of metastasis, most recent treatment prior to screening, TNM classification at study entry will be tabulated. Descriptive statistics will be used to describe tumor size at first diagnosis. Data will be summarized in the safety population by dose and overall.

Colorectal cancer history, pancreatic cancer history, and gastric/gastroesophageal junction or esophageal cancers history will not be summarized separately.

Part B

In patients who have cancer history to be reported, stage of disease at diagnosis, time since initial diagnosis (months), metastasis (yes/no), and sites of metastases (liver, peritoneum, lung, bone, regional lymph nodes, other) will be tabulated. Descriptive statistics will be used to describe the number metastases' sites.

Cancer diagnosis history will be listed.

10.6.3 OTHER PATIENT CHARACTERISTICS

Following patient characteristics will be listed:

- Medical history and current medical conditions
- Prior and concomitant medications
- Prior anticancer therapy
- Smoking history

10.7 ANALYSIS OF STUDY ENDPOINTS

This section describes analysis of primary, secondary and exploratory endpoints. All endpoints will be analyzed using planned treatments. Summaries will be presented for safety population.

Review Status: Final Version: 2.0 Version Date: 02JUN2022

10.7.1 PRIMARY ENDPOINTS

A. DLTs with OBI-888

The period for DLT is 28 days from the start of first dose of Investigational Product at Day 1 in study part A.

A DLT is defined as the occurrence of any of the following events within the first cycle of treatment and are considered to be at least possibly related to OBI-888:

- Grade 4 neutropenia
- Grade ≥ 3 febrile neutropenia with or without infection
- Grade 4 thrombocytopenia
- Grade ≥ 3 nausea and vomiting or diarrhea for more than 72 hours despite optimal supportive care
- Any Grade ≥ 3 non-hematological AE, except for nausea, vomiting, or diarrhea that does not resolve before the next infusion
- Grade 4 infusion reactions, and Grade ≥ 3 infusion reactions that recur despite decreasing infusion rate and optimal supportive care measures

DLTs will be displayed by assigned dose and cohort in a frequency table in decreasing order of incidence. DLTs will not be programmatically derived but analyzed as collected on the eCRF.

AE terms will be coded using the most current version of the Medical Dictionary for Regulatory Activities (MedDRA). AEs will be graded according to the NCI CTCAE version 4.03. All AEs unless they have been determined to be not related to study drug will be taken into consideration in determining DLTs.

B. AEs/SAEs and laboratory abnormalities as graded by NCI CTCAE version 4.03

A treatment-emergent adverse event (TEAE) is defined as an AE with onset dates on or after the start of study drug or if it is present prior to receipt of the study treatment but worsens in severity or increases in frequency on or after the first dose. AEs having both onset and end dates missing will be considered as TEAEs.

Events reported as "Unrelated" or "Unlikely related" to study drug will be considered as unrelated to the study drug. Events reported as "Possibly related", "Probably related", "Definitely related" to study drug or without relationship information will be considered as related to the treatment.

Tables will display the incidence of events (number of events, number of patients with any event, number of patients with any event in each specific system organ class [SOC], and number of patients with any event for each specific preferred term [PT]).

For each AE, only the highest grade and closest association with study drug by patient will be considered in the incidence analyses.

The following tables will be produced:

Tables by SOC and PT will be displayed for following AEs. Only those AEs marked with * will be

Review Status: Final Version: 2.0 Version Date: 02JUN2022

analyzed in the aCSR:

- DLTs
- Treatment-emergent adverse events (TEAEs)*
- TEAEs grade ≥ 3*
- TEAEs related to OBI-888*
- TEAEs leading to discontinuation of OBI-888*
- Serious TEAEs
- Serious TEAEs related to OBI-888*
- AEs leading to discontinuation of OBI-888
- SAEs leading to discontinuation of OBI-888
- TEAEs leading to death*

A table of TEAEs by SOC, PT and worst CTCAE grade (per summarization level) will be presented.

The following listings will be prepared:

- · All AEs, with DLTs flagged
- All SAEs
- AEs related to OBI-888
- AEs grade ≥ 3
- All TEAEs leading to OBI-888 discontinuation
- AEs leading to death
 - C. MTD and RP2D of OBI-888

The MTD and RP2D were identified as 20 mg/kg during SRC review.

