4.3 Clinical Studies

4.3.1 Results from OBI-888-001

As of March 2020, a total of 17 patients with locally advanced or metastatic solid tumors have been enrolled, including 14 patients in the dose escalation phase (at doses of 5, 10, and 20 mg/kg) and 3 patients in the cohort expansion phase (at the selected recommended phase II dose [RP2D] of 20 mg/kg). The dose escalation phase is complete; no dose-limiting toxicities were reported and the maximum tolerated dose was not reached. The cohort expansion phase is ongoing, with OBI-888 administered at 20 mg/kg.

There have been 8 serious adverse events (SAEs) reported from 5 patients (from all 3 dose cohorts). All SAEs were assessed by the Investigator as unrelated to OBI-888. Two SAEs were Grade 5 (both in 1 patient), and the remaining SAEs were Grade 3 in severity. No patient has discontinued the study due to treatment related adverse events (AEs). Two (2/17, 11.7%) patients died on-study, both due to disease progression. OBI-888 in doses up to 20 mg/kg have been generally well-tolerated and no safety concerns have been noted.

In general, pharmacokinetic (PK) profiles following single-dose administration were similar across patients. Pharmacokinetic analysis showed no significant accumulation in peak concentrations (C_{max}) after multiple OBI-888 doses. However, accumulation of trough concentrations was observed in most patients (12/14, 86%). The mean trough concentrations at steady state increased with increasing OBI-888 dose (3.6 µg/mL for Cohort 1 [5 mg/kg], 5.1 µg/mL for Cohort 2 [10 mg/kg], and 11.3 µg/mL for Cohort 3 [20 mg/kg]). As expected for intravenous (IV) administration, C_{max} was achieved in most patients by the end of infusion. C_{max}/D values for each dose ranged from 0.246 to 0.275, suggesting that C_{max} was dose proportional across the doses tested. AUC_{last} exhibited higher variation across the doses tested, however, mean values of AUC_{last}/D and CL were similar across the dose groups. The mean Vz ranged from 4.4 to 5.7 L across the dose groups, which is consistent with the expected distribution volume of large protein therapeutics. The t_{1/2} was similar across the dose groups (30 hours).

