The incidence of anti-drug antibody (ADA) induction was 1/5 and 1/3 in Cohorts 1 and 2 respectively. ADCC and complement dependent cytotoxicity (CDC) induction activity were observed in all post-injection serum samples, showing a positive correlation with the OBI-888 serum concentrations detected in the PK study.

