5.1.2 PART B-COHORT EXPANSION

At the time of this version of the SAP, Part A (Dose Escalation) was completed. No DLTs were observed at any dose level tested in Part A, and the MTD was not reached. Therefore, dosing in Part B was initiated at the highest dose tested in Part A (20 mg/kg OBI-888).

Part B was planned to enroll a maximum of 150 additional patients with advanced solid tumors with high Globo H expression (defined as an H-score cutoff ≥ 100 using a validated immunohistochemistry [IHC] assay) across 4 disease-specific cohorts and 1 basket cohort based on a Simon two-stage design. The first stage of Part B recruited up to 9 patients in each cohort (up to 45 patients in the first stage across all cohorts). If sufficient evidence of activity was observed in the first stage, up to 21 additional patients were to be enrolled into that cohort (up to 105 patients in the second stage across all cohorts).

Part B was conducted to obtain additional safety data, characterize the PK and PD profiles of OBI-888, obtain a preliminary assessment of the clinical activity of OBI-888 in Globo H expressing solid tumors, and inform subsequent efficacy-finding clinical development.

The following 5 cohorts of patients who had high expression of Globo H by a qualified laboratory assessment (i.e., Globo H H-score ≥ 100 using a validated IHC assay) were to be enrolled in Part B.

Cohort 1: Pancreatic cancer

Cohort 2: Esophageal cancer

Cohort 3: Gastric cancer

Review Status: Final Version: 2.0 Version Date: 02JUN2022

Cohort 4: Colorectal cancer

Cohort 5: Basket (any solid tumor type other than those included in Cohorts 1 through 4)

All patients were required to provide a tumor biopsy sample, either unstained slides (preferred) or a formalin fixed paraffin embedded (FFPE) tissue block at the initiation of screening visit for screening for Globo H overexpression and confirmation for eligibility of patients for Part B. Patients with a confirmed and documented Globo H H-score of \geq 100 were eligible for the study and were subsequently entered into the 28-day screening period to complete the remaining screening procedures.

Patients were to continue to receive treatment with OBI-888 until progressive disease, unacceptable toxicity, or a decision by the Investigator or patient to discontinue treatment.

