5.2 STUDY TREATMENT

OBI-888 was administered as an IV infusion on Days 1, 8, 15, and 22 of each 28-day cycle in Part A and Part B of the study.

For Part A (Dose Escalation), OBI-888 was given at doses of 5 mg/kg, 10 mg/kg and 20 mg/kg to the 3 dose cohorts.

For Part B (Cohort Expansion), patients were to be treated with 20 mg/kg OBI-888 since no DLTs were observed at any dose level tested in Part A, and the MTD was not reached.

Treatment was to continue until progressive disease, unacceptable toxicity, or a decision by the Investigator or patient to discontinue treatment.

OBI-888 investigational drug solution (OBI-888 drug product mixed with saline/glucose infusion solution) was to be administered as an IV infusion by the site staff.

The infusion was to be given for a duration of approximately 90-minutes (±10 minutes), for the initial two cycles (C1 and C2).

The infusion duration from Cycle 3 could be reduced, if no infusion related AEs to prior infusions occurred, to 30 minutes or 60 minutes at the discretion of the Investigator.

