7. SAMPLE SIZE AND POWER CALCULATION

This was a 2-part study: Part A Dose Escalation and Part B Cohort Expansion.

14 patients enrolled in the 3+3 dose escalation phase (Part A).

The cohort expansion phase (Part B) was to enroll up to 150 total patients based on a Simon two-stage design. The first stage was to recruit up to 9 patients in each cohort. If at least 1 objective response was observed within the first 6 cycles of therapy, a second stage recruitment was to occur with up to 21 additional patients enrolled into that cohort, for a total of up to 30 patients per cohort. If at least 4 objective responses were observed within the first 6 cycles of therapy in 30 patients, then OBI-888 was considered worthy of further evaluation in that indication. This design is based on a level of low interest for a treatment with an ORR of 5% versus a level of high interest for a treatment with an ORR of 25%. The sample size was based on a one-sided alpha of 0.05 and 90% power. The two-stage design limits the number of patients treated for a treatment with low levels of activity.

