2.2. Dose Administration

OBI-888 were administered as a 90-minute intravenous (IV) infusion on Days 1, 8, 15, and 22 of each 28-day cycle. The infusion duration may be reduced, at the investigator's discretion, to 30-60 minutes starting with Cycle 3 if the infusions in the first two cycles were well tolerated.

For Part A (Dose Escalation), OBI-888 will be given at the dose levels of 5, 10, and 20 mg/kg until MTD is determined. For Part B (Cohort Expansion), subjects were treated with 20 mg/kg OBI-888 since no DLTs have been observed at any dose level tested in Part A, and the MTD was not reached.

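### SAP 10.7.1 C records an MTD of 20 mg/kg, but the rest of the SAP and the protocol say the MTD was not reached; only the RP2D half of the sentence is consistent

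*SAP*

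**What the plan says.** SAP section 10.7.1 C is the only entry for the MTD/RP2D endpoint in the SAP's endpoint-analysis section. It reads in full: "The MTD and RP2D were identified as 20 mg/kg during SRC review".

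Other current text describes the same Part A result differently:

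- SAP 5.1.2: "No DLTs were observed at any dose level tested in Part A, and the MTD was not reached". It then explains that Part B started at 20 mg/kg because that was the top dose tested.
- SAP 5.2, giving the reason for the Part B dose: "since no DLTs were observed at any dose level tested in Part A, and the MTD was not reached".
- SAP Appendix III, section 2.2: "since no DLTs have been observed at any dose level tested in Part A, and the MTD was not reached".
- Protocol 4.3.1, reporting on a completed dose-escalation phase: "no dose-limiting toxicities were reported and the maximum tolerated dose was not reached". The protocol synopsis and sections 6.1.2 and 8.2.1 agree.

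On the RP2D there is no disagreement. Protocol 4.3.1 describes Part B patients as treated "at the selected recommended phase II dose [RP2D] of 20 mg/kg".

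**The concern.** One dose cannot be both the identified MTD and a dose at which the MTD had not been reached. Determining the MTD is a primary objective in both documents, and MTD and RP2D together form a listed primary endpoint (protocol 5.2.1, SAP 8.1).

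The two statements mean different things. A named MTD can be read as a dose bounded above by observed toxicity. An MTD not reached means that escalation ended at the highest planned dose without finding that bound. Someone using Part A to plan a higher dose or a combination would draw different conclusions from each.

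The protocol cannot simply be used to settle the matter, because its section 14 gives the SAP precedence where the two differ. Here the SAP also disagrees with itself.

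**Working it through.** The plan gives no figure to reproduce. The check applies the 3+3 rule to the reported result, then tests whether another reading reconciles the texts.

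**Step 1. Apply the escalation rule (protocol 6.1.1, SAP 5.1.1).**

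- Escalation stops when two or more of the 3 to 6 patients at a level have a DLT.
- The next lower level is then filled to six patients and becomes the MTD if at most one of the six has a DLT.
- Reported DLTs: 0 at 5 mg/kg, 0 at 10 mg/kg, 0 at 20 mg/kg.
- No level met the stopping condition, so the rule names no MTD. This matches the statements in SAP 5.1.2, 5.2 and Appendix III 2.2 and in the protocol. It does not match 10.7.1 C.

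**Step 2. Try the looser reading.** SAP 5.1.1 also describes the MTD, in parentheses, as the top dose with at most one DLT among six patients. Taken alone, this could cover 20 mg/kg if six patients were DLT-evaluable there. The documents do not state that number, but it can be bounded:

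- Part A enrolled 14 patients (SAP 7, protocol 4.3.1).
- Protocol 4.3.1: "The incidence of anti-drug antibody (ADA) induction was 1/5 and 1/3 in Cohorts 1 and 2 respectively". The same section identifies these cohorts as 5 and 10 mg/kg, so at least 5 and at least 3 patients were treated at the two lower doses.
- Maximum at 20 mg/kg: 14 − 5 − 3 = 6.
- Minimum at 20 mg/kg: 3, assumed because it is the smallest 3+3 cohort.

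The range is 3 to 6 treated. The looser reading fits only at 6, and only if all six were DLT-evaluable, which normally requires all four Cycle 1 doses.

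**Step 3. Does that reading reconcile the texts?** No. If 20 mg/kg were the MTD on that reading, the statements that the MTD was not reached would be the wrong ones. One side has to be corrected either way.

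**Step 4. What zero DLTs can support (context only).** The exact one-sided 95% upper limit for the DLT rate after 0 events in n patients is 1 − 0.05^(1/n).

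| n at 20 mg/kg | Upper limit for DLT rate |
|---|---|
| 3 | 1 − 0.05^(1/3) = 63.2% |
| 6 | 1 − 0.05^(1/6) = 39.3% |

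These limits show how little is known about the DLT rate at the top dose. The contradiction does not depend on them.

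**The case against.** The strongest reply is that this is loose terminology rather than a wrong result. Protocol 4.5 refers to the Part B dose as the MTD, protocol 6.1 asks the SRC to confirm an MTD, and the parenthetical in SAP 5.1.1 allows a highest-tolerated-dose meaning. An SRC that named 20 mg/kg in that sense would not have misread its data. This is a likely origin of the sentence, but neither document invokes that meaning in 10.7.1 C, and Step 3 shows that it moves the conflict without removing it.

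A second reply is that little follows from the sentence. This stands. The endpoint has no asterisk in SAP 8.1, so the documents do not show that it would enter the abbreviated report. The SAP also plans a DLT table and DLT flags in the AE listing, so a reader would probably see the absence of DLTs beside any named MTD. Against that, SAP section 11 does not list MTD/RP2D among the dropped analyses, and 10.7.1 C was kept in the final version.

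Third, the statements on the other side are not independent. SAP 5.2 and Appendix III 2.2 largely repeat protocol 8.2.1, and Appendix III was written from protocol version 4.0. That is fair, and the case should not rest on counting them. It rests on the escalation rule and on the SAP's inconsistency with itself. The SRC charter is a separate document and was not available to check.

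**Conclusion.** The concern holds, and it is minor. The MTD half of the sentence in SAP 10.7.1 C is wrong as written: with no DLT at any of the three doses, the design's rule gives an MTD not reached. The RP2D of 20 mg/kg is correct.

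The size is one sentence recording a primary-endpoint conclusion. No calculation, dosing decision or patient is affected, and the consequence is confined to how Part A is described.

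The conclusion relies on the reported absence of DLTs, which nothing in either document disputes. The patient count of 3 to 6 at 20 mg/kg is an inference with an assumed lower end. It bears only on how plausible the looser reading is.

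**What to change.** Replace the sentence in SAP 10.7.1 C with:

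> No DLT was observed and the MTD was not reached up to 20 mg/kg, the highest dose tested; the SRC selected 20 mg/kg as the RP2D.

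All of this content is already in SAP 5.1.2, SAP 10.7.1 C and protocol 4.3.1. The cost is one sentence, with no new data, table or analysis.

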10.7.2 SECONDARY ENDPOINTS

A. Percentage of patients with CBR according to RECIST 1.1

CBR: Defined as the proportion of patients with confirmed complete response (CR), partial response (PR) or stable disease (SD) among all the treated patients (including non-evaluable [NE] ones). A confirmed response will be defined as two or more consecutive assessments separated by at least 3 weeks. The 95% confidence interval (CI) will be estimated using the exact binomial distribution. The CBR summary table will be supported by the overall tumor response listing.

If an NE response is determined at a time point, this response will be ignored and subsequent non-NE response will be used for the confirmation. For example, the sequence of tumor assessments: PR, NE, NE, CR, SD, that had more than one consecutive NE, the third subsequent non-NE response (CR) is used as the confirmation of the first PR for best overall response derivation.

A requirement for SD is that it should be met at least once \geq 6 weeks after the first dose of trial treatment, otherwise the best response will be NE.

The criterion for confirmation of the response is summarized in the following table (Eisenhauer et al, 2009):

Overall response first time point	Overall response subsequent time point	Best overall response
CR	CR	CR
CR	PR	SD, PD or PR [1]
CR	SD	SD provided minimum criteria for SD duration met, otherwise PD
CR	PD	SD provided minimum criteria for SD duration met, otherwise PD
CR	NE	SD provided minimum criteria for SD duration met, otherwise NE
PR	CR	PR
PR	PR	PR
PR	SD	SD
PR	PD	SD provided minimum criteria for SD duration met, otherwise PD
PR	NE	SD provided minimum criteria for SD duration met, otherwise NE
NE	NE	NE

^[1] If a CR is truly met at first timepoint, then any disease seen at a subsequent timepoint, even disease meeting PR criteria relative to baseline, makes the disease PD at that point (since disease must have re-appeared after CR). Best response would depend on whether minimum duration of SD was met. However, sometimes 'CR' may be claimed when subsequent scans suggest small lesions were likely still present and in fact the patient had PR, not CR at the first timepoint. Under these circumstances, the original CR should be changed to a PR and the best response is PR.

Overall tumor response (not to be programmatically derived and collected on eCRF) will be listed by assigned dose, cohort, and visit.

B. Percentage of patients with ADAs in blood

The number and percentage of patients with positive ADAs in the blood will be summarized for the safety population.

C. PK and PD parameters of OBI-888

Pharmacokinetic Analysis

PK and PD analyses will be conducted by OBI Pharma, Inc. Please refer to statistical analysis plan developed for PK and PD parameters (Appendix III).

10.7.3 EXPLORATORY ENDPOINTS

- Globo H and related glycan expression in tumor tissue by IHC
- ADCC and CDC
- Identify potential predictive markers by IHC or molecular analysis
- TILs, including NK cells, and PD-L1 expression in tumor tissue samples by IHC

Review Status: Final Version: 2.0 Version Date: 02JUN2022

Version Date: 02JUN202
 KIR, HLA, and Fc receptor gamma genotype

• Glycan analysis of OBI-888

The above analyses will be conducted by OBI Translational Biology (or their designee). Details of these analyses will be provided in separate document(s). The results will be compiled into a separate appendix in Section 14 of the aCSR.

10.8 SAFETY ENDPOINTS

This section describes the safety endpoints that are not part of the primary, secondary, or exploratory endpoints previously described in section 10.7.

All safety endpoints will be analyzed using the safety population based on treatments the patients actually received during the study.

Safety will be evaluated by presenting summaries of exposure to study treatment, laboratory evaluations (hematology, chemistry, coagulation, and urine analysis), vital signs, and other parameters.

